4. PATIENT ENROLLMENT AND EVALUATION

4.1. Enrollment

Patients will be registered for this trial using a web-based database that will be utilized for collection of all clinical and laboratory data.

Follow this procedure:

- 1. An authorized user at the clinical center completes the initial screening by entering patients' demographics.
- 2. If the patient signs the informed consent and assent (if applicable), a study number is generated.
- 3. A visit schedule based on enrollment date is displayed for printing.

Subjects enrolled when they are less than 18 years of age will be reconsented at the first office visit following their 18th birthday. Data and specimens collected from these subjects prior to their 18th birthday may continue to be used without this additional consent; however, no clinical data or specimens from after the 18th birthday may be collected or utilized until the re-consenting process has been completed.

4.2. Study monitoring

The follow-up schedule is outlined in Table 3 (see below).

Table 3: Required assessments													
	All allogeneic HCT, day pre/post-HCT							post-	НСТ	GVHD +	Day post- GVHD systemic therapy		Chimerism
	-7	7	14	21	28	56	100	180	360	Onset (0)	28	56	If Standard of Care in Center
Biopsy of involved tissue (as part of routine clinical care, not research)										х			
Acute GVHD evaluation ^		Х	Х	Х	Х	Х	Х	Х		Х	Х	Х	
Chronic GVHD evaluation ^							Х	Х	Х				
Steroid dose		Х	Х	Х	Х	Х	Х	Х		Х	Х	Х	
Other GVHD medications, doses, and drug levels collected as part of clinical care		x	x	х	x	х	х	x	x	х	х	x	
Blood Samples*	Х	Х	Х	Х	Х	Х	Х	Х	Х	Х	Х		
Saliva DNA (if WBC < 400/µL)	х					Х							
Chimerism (% donor) ‡ **													Х

*Up to day 28, sample collection may be ± 4 days from the target day to allow for scheduling flexibility, holidays, etc...

*Day 100,180, and 360, sample collection will be collected at the clinic visit closest to the scheduled time point to allow for scheduling flexibility, holidays, etc...

*GVHD onset sample will be collected within a 48 hour window of systemic treatment initiation if subject is inpatient

‡ Donor chimerism results recorded at the time nearest to each sample collection will be noted.

^ Refer to Appendix D for GVHD assessment forms

** Will only collect data if already being done as standard of care at center

The timing of follow-up visits is based on the date of BMT and then on the

date of onset of GVHD for post-GVHD assessments.

Assessments

- Baseline weight
- For all, complete acute GVHD staging and grading information including assessment of rash, diarrhea, nausea/vomiting, liver function and weight at day
 - 7, 14, 21, 28, 56, 100, and 180 post-HCT
- If GVHD or GVHD-like symptoms,
 - recommended biopsy of involved tissue (this is standard of care, not research)
 - Complete acute GVHD staging and grading information including assessment of rash, diarrhea, nausea/vomiting, liver function and weight at onset of symptoms and 28 and 56 days post-systemic GVHD therapy
 - Steroids dose weekly until day 56
 - $_{\odot}$ Samples for laboratory studies at day -7, 7, 14, 21, 28, 56,100 and 180

post-HCT and at onset of GVHD symptoms, and 28 days post-systemic

- GVHD therapy
- Chronic GVHD evaluation at day 100, 180 and 360
- Infections requiring therapy up to 360 days post-HCT

Sample Collection

Samples will be collected at a time when clinical samples are being collected as well if possible. That is, this protocol will NOT require an additional procedure or for a patient's central venous line to be accessed at a time when these things are not being done as part of routine clinical care.

Blood will be collected as part of this study for use in evaluation of biomarkers of HSCT-related toxicities and outcomes and future unspecified research.

 Blood will be collected using the schedule detailed above: day -7 and the following post-transplant days: 7, 14, 21, 28, 56, 100, 180, and 360. Please note that the above blood draw schedule is a target only. Subjects will never be required to come for a clinic visit specifically to have samples collected for the purposes of this study. As such sample

samples collected for the purposes of this study. As such, sample time- points are targets and samples will be collected at the time closest to the target time when collection is feasible. In addition, during inpatient periods, sample collection will take place on the business day closest to

the day scheduled per protocol (to allow for flexibility around weekends and holidays).

- Blood will also be collected at onset of acute GVHD and at day 28 after initiation of steroid therapy.
- In addition, blood will be collected at the onset of other changes in status, which may be clinically significant (such as suspected sinusoidal obstruction syndrome, respiratory distress, relapse, etc.).
- Blood volume to be collected:

Please note cumulative collection volumes at various points in time of participation are summarized in the table below and are detailed for patients >40 kg in text immediately below for clarity.

- Patients > 40 kg: up to 15 mL per time point)
 - 9 scheduled collections in year one = 135 mL
 - 2 scheduled collections in patients who develop acute GVHD = 30 mL
 - Maximum additional blood draws at the time of developing other complications will be set at **four**.
 - 9 scheduled collections + 2 additional collections GVHD collections (if applicable) + maximum of four additional collections with other complications = 15 collections maximum = maximum blood draw of 225 mL.

	Patient Size on Enrollment			
	> 40 kg	25-40 kg	10-25 kg	<10 kg
Maximum volume of each scheduled blood draw	15 mL	10 mL	7.5 mL	5 mL
Maximum volume of blood of each blood draw if develops acute GVHD	15 mL	10 mL	7.5 mL	5 mL
Maximum volume of blood with each complication	15 mL	10 mL	7.5 mL	5 mL
Maximum volume for scheduled blood draws (9 collections)	135 mL	90 mL	67.5 mL	45 mL
Maximum blood volume if develops acute GVHD (2 collections)	30 mL	20 mL	15 mL	10 mL
Maximum blood volume for other complications (4 collections)	60 mL	40mL	30 mL	20 mL
Maximum volume collected in year one (scheduled plus collections with complications)	225 mL	150 mL	112.5 mL	75mL

Table 4: Summary of maximum blood volume to be collected for this study

*Cumulative blood volume will be monitored for each subject and individual blood draws will be decreased as needed to maintain annual cumulative blood collection of <10% of total blood volume.

Also note, for pediatric patients, we expect patient weights to increase over time due to normal growth and as such, updated patient weights will be used to re-calculate permitted blood volume collections every six months.

GVHD scoring

Acute GVHD

A sample Acute GVHD data record for use in this trial is attached below.

Today's Clinical Acute GVHD Assessment						
Today's date Patient ID		Karnofsky/Lansky				
Codes		Differential diagnosis				
0 1 2 3 4		GVHD Drug Cond Infect TPN VOD Other				
		Rxn Reg				
Skin 🗆 🗆 🗆 🕬	oody rash:					
Liver 🗆 🗆 🗆 🗆 Curr	ent bili: [Lower				
GI 🗆 🗆 🗆 🗆 Vol:		□ □ □ □ Upper GI				
		Systemic				
agents: 🗌 CSA 🗌	Tacrolimus	🗌 Infliximab 🛛 🗍 Daclizimab				
Pentost	atin 🛛 Sirolimu	s				
Prednis	one 🗌 Methylp	rednisolone 🗌 Ontak 🗌 Other				
Current steroid dose: Prednisone	mg/	kg/day; Methylprednisolone mg/kg/day				
Has the steroid dose been increased to $\ge 2.5 \text{ mg/kg/day}$ of prednisone (or 2 mg/kg/day methylpred)? \square YES \square NO If yes, data dose increased						
Topical agents: Skin topical steroids: YES NO; Non-absorbed oral steroids (e.g. Budesonide, Entocort) Image: Chronic GVHD: Does the patient have evidence of chronic GVHD? YES NO						
Codes Skin	Liver (bilirubin)	Lower GI (stool output/day) Upper GI				
0 No rash	≤ 2 mg/dl	Adult: < 500 ml/dayNo protracted nausea andChild: < 10 ml/kg/day				
1 Maculopapular rash < 25% BSA	2.1-3 mg/dl	Adult: 500–1000 ml/dayPersistent severe nausea, vomiting with a positive upper GI biopsy				
2 Maculopapular rash 25 – 50% BSA	3.1-6 mg/dl	Adult: 1001-1500 ml/day Child: 20 – 30 ml/kg/day				
3 Generalized erythroderma (>50% BSA)	6.1-15 mg/dl	Adult: >1500 ml/day Child: > 30 ml/kg/day				
4 Generalized erythroderma (>50% BSA) plus bullous formation and desquamation > 5% BSA	>15 mg/dl	Severe abdominal pain with or without ileus, or grossly bloody stool or melena (regardless of stool volume)				
Signature		Date				

Chronic GVHD

Patients developing symptoms of chronic GVHD will have their symptoms recorded on the chronic GVHD scoring form (**Appendix D**) at the scheduled follow-up visits:

Table 4: Definite and Possible Manifestation of Chronic GVHD*							
Organ system	Definite manifestations of chronic GVHD	Possible manifestations of chronic GVHD					
Skin	Scleroderma (superficial and fasciitis), lichen planus, vitiligo, scarring alopecia, hyperkeratosis pilaris, contractures from skin immobility, nail bed dysplasia	Eczematoid rash, dry skin, maculopapular rash, hyperpigmentation, hair loss					
Mucous Membranes	Lichen planus, non-infectious ulcers, corneal erosions, non-infectious conjunctivitis	Xerostomia, keratoconjunctivitis sicca					
GI tract	Esophageal strictures, steatorrhea	Anorexia, malabsorption, weight loss, diarrhea, abdominal pain					
Liver	None	Elevation of alkaline phosphatase, transaminitis, cholangitis, hyperbilirubinemia					
GU	Vaginal stricture, lichen planus	Non-infectious vaginitis, vaginal atrophy					
Musculoskeletal/serosa	Non-septic arthritis, myositis, myasthenia, polyserositis, contractures from joint immobilization	Arthralgia					
Hematologic	None	Thrombocytopenia, eosinophilia, autoimmune cytopenias					
Lung	Bronchiolitis obliterans	Bronchiolitis obliterans with organizing pneumonia, interstitial pneumonitis					

*From BMTCTN MOP chapter 2

Pediatric considerations

Children with chronic GVHD can present with skin, GI, eye or systemic disease leading to failure to thrive, persistent immunodeficiency, or pulmonary disease. Chronic "eczema' or dry skin are common manifestations of mild chronic GVHD of skin. Liver disease can present as asymptomatic hyperbilirubinemia or elevated alkaline phosphatase. As children can have marked elevations in alkaline phosphatase during growth spurts, children with this laboratory abnormality should have a fractionated alkaline phosphatase to confirm that the band is from the liver and not from bone before a diagnosis of chronic GVHD is made. Children with chronic GVHD of the upper GI tract may have chronic anorexia or poor growth due to malabsorption. Rather than losing weight, children may "fall off" their growth curve with decreased gains in height or weight velocity. In children < 2 years of age, this may also affect growth of head circumference. Chronic GVHD may also cause persistent low or intermediate immunodeficiency. In addition to increasing the risk of opportunistic infection, this may cause GI dysfunction and lead to malabsorption, low IgG (due to protein losing enteropathy), lactose deficiency, and poor growth. Duodenal intubation with quantitation of pancreatic enzymes is useful in these children. If pancreatic enzymes are low, children may benefit from supplementation of pancreatic enzymes.

See Appendix D for a sample of chronic GVHD data record for use in this trial.

Summary of Required Assessments

- For all subjects
 - complete acute GVHD staging and grading information including assessment of rash, diarrhea, nausea/vomiting, liver function and weight at day 7, 14, 21, 28, 56, 100, and 180 post-HCT
 - Chronic GVHD evaluation at day 100, 180 and 360 post-HCT (please refer to Appendix D for GVHD assessment forms)
 - Infections requiring therapy up to 360 days post-HCT
 - Baseline weight
 - Blood samples for laboratory studies and future use at day -7, 7, 14, 21, 28, 56,100,180, and 360 post-HCT
- For subjects who develop GVHD or GVHD-like symptoms,
 - recommended biopsy of involved tissue (this is standard of care, not research)
 - Complete acute GVHD staging and grading information including assessment of rash, diarrhea, nausea/vomiting, liver function and weight at onset of symptoms and 28 and 56 days post-systemic GVHD therapy
 - Steroid dosing information weekly until day 56 after initiation of steroids
 - Blood samples for laboratory studies and future use at onset of GVHD symptoms and 28 days post-systemic GVHD therapy initiation

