3.4. Studies of GVHD Biomarkers

If consent for research samples is obtained, blood samples will be collected on Day -7, day 7, day 14, day 21, day 28, day 56, day 100, day 180, and day 360 post-HCT, as well as at appearance of clinical symptoms suggestive of acute GVHD and that triggers systemic steroid treatment. These samples will be analyzed for the seven-protein biomarker panel. Remaining plasma sample aliquots will be stored for future biomarker studies. Additional, whole blood collected from the recipient on day 56 post-HCT (representing the donor DNA) and day -7 whole blood or saliva DNA (if white blood cells count < $400/\mu$ L) (representing recipient DNA) will be collected, frozen and stored for future genomic studies. Donor chimerism results recorded at the time nearest to each sample collection will be noted. Please note all sample collection days are targets with collection of samples on the closest business day to the suggested day being acceptable.

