Descriptive statistics of demographic variables and NRM including frequencies and percentages were summarized by age groups (≤10 years vs. >10 years). Chi-square or nonparametric Mann-Whitney tests were performed to assess potential differences in demographic variables between age categories. Cumulative incidences of NRM and aGVHD were analyzed with relapse as a competing risk. The Aalen-Johansen estimator was used to nonparametrically estimate the cumulative incidence function (CIF) of NRM and aGVHD. In order to account for the time-dependent biomarker values (pre-HCT, and at 7, 14 and 21 days post-HCT) we employed landmark analyses. Separate CIFs were estimated by biomarker category (above and below the median at day 21 for the whole cohort which is also a clinically relevant threshold based on previous studies) for each landmark time point, the biomarker value at this landmark time point was considered and, also, patients who survived until that landmark. To statistically evaluate the difference of the CIFs of NRM and GVHD between the two biomarker groups, while accounting for the left truncation at each landmark point, we used two-sample nonparametric linear tests. To perform a multivariable competing risks analysis, the biomarker values for all landmarks points were stacked into a single variable and a semiparametric proportional cause-specific hazards model was fitted to the data. Hazard ratios with confidence intervals were reported to demonstrate effect size. To account for the potential association across the repeated records for each patient we used a proper sandwich variance estimator in a population-averaged estimation framework. For each model, the interaction between the biomarker and the landmark quantified the change of the association between each biomarker and the outcome over time. If the interaction was not statistically significant then there was no evidence that the association between the biomarker and the outcome changed over time. The models also included an interaction term between the biomarker and patient's age. A significant biomarker by age interaction indicated that the association between the biomarker and the outcome differed between age groups. Multivariable analyses were conducted using the following covariates: race/ethnicity, malignant disease, graft source, and aGVHD prophylaxis. A cause-specific analysis that included type of malignant disease type, disease risk index, and disease status at HCT was also performed in the subgroup of patients with malignant diseases. We sought to determine if the combination of biomarkers improves the predictive accuracy for NRM.

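### The SAP has no rule for samples drawn up to 4 days after a landmark; if entry is at the nominal day, a marker drawn after aGVHD onset can count as predicting it

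*Protocol*

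**What the plan says.** Three places in the protocol bear on when an early sample may be drawn.

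- Section 4.2, Table 3 footnote: "Up to day 28, sample collection may be ± 4 days from the target day to allow for scheduling flexibility".
- Section 4.2, Sample Collection: "the above blood draw schedule is a target only", and "samples will be collected at the time closest to the target time when collection is feasible". The same paragraph holds inpatient draws to the nearest business day and states that nobody must attend solely for sampling.
- Section 3.4: "collection of samples on the closest business day to the suggested day being acceptable".

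The SAP, under Statistical analysis, sets the landmarks: "In order to account for the time-dependent biomarker values (pre-HCT, and at 7, 14 and 21 days post-HCT) we employed landmark analyses". Its rule for who enters is: "for each landmark time point, the biomarker value at this landmark time point was considered and, also, patients who survived until that landmark". The tests of the cumulative incidence functions (CIFs) for NRM and aGVHD are made "while accounting for the left truncation at each landmark point". The values from all landmarks are then stacked in a cause-specific hazards model with a biomarker-by-landmark interaction.

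The SAP does not mention the actual draw date. It does not say what happens to a late sample, or whether a patient must be free of aGVHD when the sample is drawn.

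**The concern.** A landmark analysis is sound when the exposure is known at the landmark and follow-up starts there. A sample labelled day 14 but drawn on day 18 breaks that condition if the clock starts on day 14. The patient had to live to day 18 to be classified, whereas one who died on day 16 before being sampled has no value and drops out. That is immortal time.

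For aGVHD there is a second problem. The stated entry condition is survival, not freedom from aGVHD. A patient whose aGVHD begins on day 22 and whose day-21 sample is drawn on day 24 contributes a marker level measured during the disease as though it had preceded it. Protocol section 1.3 reports that REG3α and the four-protein panel, which includes TNFR1, are higher in patients with GVHD, and both REG3α and TNFR1 are SAP markers. A diagnostic signal could therefore be read as a predictive one, when early prediction is what the landmark analyses are meant to test.

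**Working it through.** The documents give no figure for this effect, so there is none to reproduce. The check sizes it from stated inputs where they exist and from declared assumptions otherwise.

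**Inputs from the documents.** Window ±4 days (protocol 4.2). 415 patients (SAP). Planning rates of 0.26 for day-180 NRM and 0.50 for aGVHD (protocol Appendix C). The 0.26 is a post-therapy rate, so it serves as an upper value for the whole cohort. Typical aGVHD onset is 2 to 8 weeks, taken as days 14 to 56 (protocol 1.1).

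**Assumptions.** Lower rates of 10% for NRM and 30% for aGVHD. Late share of 25%, 50% or 100%, with delays of 1 to 4 days equally likely (mean 2.5). Half of patients in the high-marker group.

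**Step 1: latest permitted draw.** 7 + 4 = day 11; 14 + 4 = day 18; 21 + 4 = day 25. The pre-HCT sample is not materially affected: −7 + 4 = day −3, still before transplant.

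**Step 2: events in a 4-day gap.**
- NRM with constant hazard: 415 × [1 − (1 − r)^(4/180)]. For r = 0.10 this is 415 × 0.00234 = 1.0; for r = 0.26 it is 415 × 0.00667 = 2.8.
- aGVHD with onset uniform over 42 days: 415 × 0.30 × 4/42 = 12; 415 × 0.50 × 4/42 = 20.

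**Step 3: effect on NRM.** Simulation from day 21, 2,000,000 patients per scenario, without competing relapse, true hazard ratio 2.0.

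| Scenario | HR, entry at nominal day | HR, entry at draw |
|---|---|---|
| Lateness unrelated to marker (50% or 100% late) | about 2.00 | about 2.00 |
| All high-marker draws late, no low-marker draw late | 1.97 | 2.01 |
| Same, hazard tripled in the first 4 days | 1.91 | 1.95 |

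With lateness unrelated to the marker, day-180 cumulative incidence is understated by about 0.15 to 0.3 percentage points, or 0.5 to 1.0 if the early hazard is tripled.

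**Step 4: effect on aGVHD at day 21.** Assume 35% of patients have onset, uniform over days 21 to 56.
- Post-onset share if all draws are late: 0.35 × 2.5/35 = 0.025, or 415 × 0.025 = 10.4 patients. At 50% late it is 5.2, and at 25% it is 2.6. These counts treat all 415 as at risk on day 21 and scale with the 35%.
- Suppose the true risk ratio is 1.00, all draws are late, and every post-onset low marker has risen to high. Then 0.5 × 0.025 = 0.0125 of patients move group. High: (0.175 + 0.0125)/(0.5 + 0.0125) = 0.366. Low: (0.175 − 0.0125)/(0.5 − 0.0125) = 0.333. Ratio 1.10.
- At 25% late with half of such markers rising, the moved share is 0.5 × 0.00625 × 0.5 = 0.00156. The ratio is (0.17656/0.50156)/(0.17344/0.49844) = 1.01.
- Simulation gives the same range, and for a true risk ratio of 2.0 it gives 2.02 to 2.15. Dropping post-onset draws returns 1.00 for the first case and 2.01 to 2.03 for the second.

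**The case against.** The best defence is that the SAP never says entry is at the nominal day or that late samples were used at the earlier landmark. A reader might infer that immortal time in the reported analyses has been demonstrated. The documents do not support that: they give no draw dates and no handling rule. What stands is narrower. Fixed landmarks, left truncation at those landmarks and a survival-only condition point naturally to nominal-day entry, and nothing in the SAP prevents it.

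Second, the 4 days are a permitted maximum. The window is two-sided, draws on or before the landmark create no immortal time, and inpatient draws are held to the nearest business day. Many delays may be short. This stands and limits the likely size, although the target-only wording leaves outpatient draws without a firm limit.

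Third, guaranteed survival applies to both marker groups and largely cancels in the NRM comparison. This also stands, as Step 3 shows.

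Fourth, if left truncation is applied with aGVHD itself as the event, patients with onset before the landmark are already out. That is fair, but it does not remove onsets between landmark and draw, which are the ones counted in Step 4.

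A reader might also see a bias in the overlap of the windows on days 10–11 and 17–18. Overlap alone does not create one: a day-14 sample drawn on day 10 precedes its landmark.

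**Conclusion.** The concern holds as a gap in the landmark rule with a modest consequence. Read naturally, the SAP allows a marker drawn after the landmark, and even after aGVHD onset, to be treated as known at the landmark. For NRM the effect on the comparison is negligible, a difference of 0.04 in the hazard ratio in the most adverse scenarios examined. For aGVHD the bias exaggerates the apparent predictive value of a marker that rises with disease: 1.00 becomes 1.01 to 1.10, with about 3 to 10 post-onset values among 415 at day 21.

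These sizes rest on the assumed late share, uniform onset, 35% incidence after day 21, and a rise in the marker after onset in half to all of the patients concerned. If the recorded draw dates show few late samples, the effect is smaller still. The finding is worth correcting because the error is systematic and easily removed. It does not show that the NRM results are unreliable.

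**What to change.** 1. In the left-truncated CIFs and the stacked model, start each patient's follow-up for a landmark at the later of the landmark and the actual draw date. Keep the nominal landmark label for the biomarker-by-landmark interaction.
2. In the aGVHD analyses, restrict the risk set to patients free of aGVHD at that entry time. Post-onset draws then drop out.
3. Report the distribution of draw days for each landmark.

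The methods the SAP already names accommodate delayed entry, so no new sampling or assay is needed, provided draw dates were recorded. Protocol section 4.5 plans electronic forms that track sample collection. The cost is some recoding, the loss of a few records from the aGVHD analyses (about 3 to 10 at day 21 under the assumptions above), and patient-specific entry times in a model built on fixed landmarks. The aGVHD estimates would then describe risk from the time of sampling in patients still free of aGVHD, and the text should say so.
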